8.1.4. Telephone Call T3.1 (Visit 3 + 2 to 5 Weeks)

One week after delivery of the new supplies to the participant, the study site will telephone the participant to check the supplies have been received and any old supplies returned. The participant will be asked about any AEs and changes in concomitant medications at this call and any AEs or changes in concomitant medication reported will be recorded in the eCRF.

8.1.5. Visit 4 (Titration Visit - Week 10 \pm 1 Week)

Six weeks after the previous visit (± 1 week), participants will be requested to attend the study site for testing of androgen levels (if necessary this visit can be conducted as a domiciliary visit). Prior to the visit, the site staff should contact the participant to check that 'stress dosing rules' have not been applied in the 5 days preceding the visit date. If 'stress dosing rules' have been applied, then the visit should be postponed until the participant has been receiving no stress dosing medication for 5 days. The participant will be instructed to bring any empty packaging and any unused study medication and the emergency treatment pack with them to the visit for accountability purposes (note: participants take unused study medication and emergency treatment pack back home with them to use until the dose titration

decision is made and new study medication dispensed). The participants will be told not to take their morning dose of study medication before attending for the visit (the morning dose will be taken after the 08:00 androgen sample and optional saliva sample [where applicable]). Male participants will be asked not to take multivitamins or dietary supplements containing biotin or vitamin B7 for 12 hours prior to the visit (to avoid interference with LH test results).

The following assessments will be carried out and recorded at this visit:

- Record the details of the participant's glucocorticoid doses for the previous 24 hours and throughout the visit
- Participants will be asked about any AEs (including events considered to be of unexpected benefit) and concomitant medications changes since the last visit
- Vital signs (BP, HR, respiratory rate and body temperature. BP to be recorded after the participant has been semi-supine for 10 minutes)
- Abbreviated physical examination (if indicated by AEs)
- Height, weight and waist circumference will be measured
- Assessment of menstrual cycle changes in all pre-menopausal women
- Assessment of hirsutism by female participants using a VAS and by Investigators using Ferriman-Gallwey score (the Investigator can assess this via a video call if a domiciliary visit is conducted for this visit [within ±2 days of the domiciliary visit])
- Assessment of acne by female participants using a VAS and by the Investigators using the GEA (the Investigator can assess this via a video call if a domiciliary visit is conducted for this visit [within ±2 days of the domiciliary visit])
- Assessment of alertness by the participant using a VAS
- Signs and symptoms of adrenal insufficiency using the adrenal insufficiency checklist (the Investigator must complete the checklist even if a domiciliary visit is conducted for this visit)
- The following questionnaires will be completed: SF-36®, MAF, and EQ-5D-5L™
- Blood sample for HbA1c, FSH, osteocalcin, LH, and routine biochemistry and hematology
- Urinalysis
- Pregnancy test in WOCBP (either urine or blood as per the site's usual practice)
- Review of emergency treatment pack for compliance
- Blood sampling for measurement of androgen levels (17-OHP and A4) at 08.00 (pre-dose) and 13.00 hours
- Saliva samples collected for exploratory analysis at 08.00 (pre-dose) and 13.00 hours (optional).

The androgen blood samples are to be taken within ±30 minutes of the stated timepoints, with the exact sampling times recorded in the eCRF. Half the sample will be sent for analysis at the central laboratory, with the remaining half initially retained at the site before being sent to the central laboratory and then on to the biobank for long-term storage and possible future research.

The participant will be asked to attend the clinic for Visit 5 in 6 weeks' time. Participants will be reminded to complete the alertness VAS on a weekly basis in the morning before their morning dose of study medication. The same day of the week should be used each week.

Participants will be discharged once the last androgen sample has been taken and all other assessments have been completed.

Following determination of the Visit 4 androgen levels and completion of the adrenal insufficiency checklist, a decision will be made by an independent blinded physician as to whether the participant's dose should be adjusted, and the appropriate IMP packs will be sent to the participant, either to collect from their local study site or sent directly to the participant's home (note: the changes will also include the relevant changes to the placebo capsules to maintain the blinding). The treatment packs for each participant will always contain the same number of capsules as the previous supplies (with placebo capsules masking any changes), thus ensuring the participant is not aware of any dose changes. Participants will be asked to record the dose, date and time they took the first dose of the revised study medication (if applicable) in their electronic participant diary.

Any dose titrations should be made within 2 to 3 weeks of the visit (dependent on the laboratory turnaround time of androgen samples, the time needed by the independent blinded physician to evaluate the data, and for the supplies to be sent to the participant).

8.1.6. Telephone Call T4.1 (Visit 4 + 2 to 5 Weeks)

One week after delivery of the new supplies to the participant, the study site will telephone the participant to check the supplies have been received and any old supplies returned. The participant will be asked about any AEs and changes in concomitant medications at this call and any AEs or changes in concomitant medication reported will be recorded in the eCRF.

8.1.7. Visit 5 (Titration Visit - Week 16 ± 1 Week)

Six weeks after the previous visit (\pm 1 week), participants will be requested to attend the study site for testing of androgen levels. Prior to the visit, the site staff should contact the participant to check that 'stress dosing rules' have not been applied in the 5 days preceding the visit date. If 'stress dosing rules' have been applied, then the visit should be postponed until the participant has been receiving no stress dosing medication for 5 days. It is mandatory that this visit is conducted at the study site, although if necessary in some cases, IMP at this visit can be delivered to the participant's home. The participant will be instructed to bring any empty packaging and any unused study medication and the emergency treatment pack with them to the visit for accountability purposes (note: participants take unused study medication and emergency treatment pack back home with them to use until the dose titration decision is made and new study medication dispensed). The participants will be told not to take their morning dose of study medication before attending for the visit (the morning dose will be taken after the 08:00 hour androgen sample and optional saliva sample [where applicable]). Male participants will be asked not to take multivitamins or dietary supplements containing biotin or vitamin B7 for 12 hours prior to the visit (to avoid interference with LH test results).

The following assessments will be carried out and recorded at this visit:

- Record the details of the participant's glucocorticoid doses for the previous 24 hours and throughout the visit
- Participants will be asked about any AEs (including events considered to be of unexpected benefit) and concomitant medications changes since the last visit

- Vital signs (BP, HR, respiratory rate and body temperature. BP to be recorded after the participant has been semi-supine for 10 minutes)
- Abbreviated physical examination (if indicated by AEs)
- Height, weight and waist circumference will be measured
- Assessment of menstrual cycle changes in all pre-menopausal women
- Assessment of hirsutism by female participants using a VAS and by Investigators using Ferriman-Gallwey score
- Assessment of acne by female participants using a VAS and by Investigators using the GEA
- Assessment of alertness by the participant using a VAS
- Signs and symptoms of adrenal insufficiency using the adrenal insufficiency checklist
- The following questionnaires will be completed: SF-36®, MAF, and EQ-5D-5L™
- Blood sample for HbA1c, FSH, osteocalcin, LH, and routine biochemistry and hematology
- Urinalysis
- Pregnancy test in WOCBP (either urine or blood as per the site's usual practice)
- Review of emergency treatment pack for compliance
- Blood sampling for measurement of androgen levels (17-OHP and A4) at 08.00 (pre-dose) and 13.00 hours
- Saliva samples collected for exploratory analysis at 08.00 (pre-dose) and 13.00 hours (optional).

The androgen blood samples are to be taken within \pm 30 minutes of the stated timepoints, with the exact sampling times recorded in the eCRF. Half the sample will be sent for analysis at the central laboratory, with the remaining half initially retained at the site before being sent to the central laboratory and then on to the biobank for long-term storage and possible future research.

Participants will be asked to attend the clinic for Visit 6 in approximately 12 weeks' time. Participants will be reminded to complete the alertness VAS on a weekly basis in the morning before their morning dose of study medication. The same day of the week should be used each week. Participants will be discharged once the last androgen sample has been taken and all other assessments have been completed.

Following determination of the Visit 5 androgen levels and completion of the adrenal insufficiency checklist, a decision will be made by an independent blinded physician as to whether the participant's dose should be adjusted, and the appropriate IMP packs will be sent to the participant, either to collect from their local study site or sent directly to the participant's home (note: the changes will also include the relevant changes to the placebo capsules to maintain the blinding). The treatment packs for each participant will always contain the same number of capsules as the previous supplies (with placebo capsules masking any changes), thus ensuring the participant is not aware of any dose changes. Participants will be asked to record the dose, date and time they took the first dose of the revised study medication (if applicable) in their electronic participant diary.

Any dose titrations should be made within 2 to 3 weeks of the visit (dependent on the laboratory turnaround time of androgen samples, the time needed by the independent blinded physician to evaluate the data, and for the supplies to be sent to the participant).

8.1.8. Telephone Call T5.1 (Visit 5 + 2 to 5 Weeks)

One week after delivery of the new supplies to the participant, the study site will telephone the participant to check the supplies have been received and any old supplies returned. The participant will be asked about any AEs and changes in concomitant medications at this call and any AEs or changes in concomitant medication reported will be recorded in the eCRF.

8.1.9. Telephone Call T5.2 (Week 22 ± 2 Weeks)

A telephone call will be made to all participants approximately 4 weeks after the last telephone call. All participants will be asked about any AEs or any other problems plus any changes in concomitant medications since their last visit. Any AEs or changes in concomitant medications will be recorded in the eCRF.

8.1.10. Visit 6 (End of Study/Early Withdrawal Visit - 28 Weeks + 1 Week From Randomization or at Point of Discontinuing Treatment or Withdrawing From the Study)

This visit is required for all participants either 28 weeks after randomization or at the time a participant withdraws early from treatment or from the whole study. The last dose of study medication will be taken in the morning of the last dosing day after the 08:00 hour androgen sample and optional saliva sample (where applicable) are collected. It is mandatory that this visit is conducted at the study site. If a participant who was enrolled under an earlier version of the protocol (where the study was up to 52 weeks in duration) had attended Visit 5 at Week 16 and is ongoing treatment, they must continue taking the study medication and must return at 28 weeks for the EOS (Visit 6) assessments. If they have already had more than 28 weeks of treatment then they must return as soon as possible (but not within 4 weeks of previous blood sampling) for the EOS (Visit 6) assessments according to this amendment. In the case of early withdrawal from treatment or from the study, as many assessments as possible should be completed within 48 hours of the last dose of the study medication. If the participant only discontinues study treatment, they should remain in the study where possible and be followed for safety assessments until the scheduled EOS visit (note: no efficacy endpoints will be collected once the assessments detailed for Visit 6 [early withdrawal] are completed).

Prior to the visit, the site staff should contact the participant to check that 'stress dosing rules' have not been applied in the 5 days preceding the visit date. If 'stress dosing rules' have been applied, then the visit should be postponed until the participant has been receiving no stress dosing medication for 5 days. The participant will be instructed to bring any empty packaging and any unused study medication and the emergency treatment pack with them to the visit for accountability purposes. The participants will be told not to take their morning dose of study medication before attending for the visit (the morning dose will be taken after the 08:00 hour androgen sample and optional saliva sample [where applicable]). Male participants will be asked not to take multivitamins or dietary supplements containing biotin or vitamin B7 for 12 hours prior to the visit (to avoid interference with LH test results) and also not to ejaculate for the preceding 3 days for the sperm count assessment (if the participant has consented to this assessment).

The following assessments will be carried out and recorded at this visit:

- Record the details of the participant's glucocorticoid doses for the previous 24 hours and throughout the visit
- Participants will be asked about any AEs and concomitant medications changes since the last visit
- Vital signs (BP, HR, respiratory rate and body temperature. BP to be recorded after the participant has been semi-supine for 10 minutes)
- Full physical examination
- Height, weight, and waist circumference will be measured
- Assessment of menstrual cycle changes in all pre-menopausal women
- Assessment of hirsutism by female participants using a VAS and by Investigators using Ferriman-Gallwey score
- Assessment of acne by female participants using a VAS and by the Investigators using the GEA
- Assessment of alertness by the participant using a VAS
- Assessment of treatment preference (randomized treatment compared to their usual medication) using a VAS
- Signs and symptoms of adrenal insufficiency using the adrenal insufficiency checklist
- The following questionnaires will be completed: SF-36®, MAF, and EQ-5D-5L™
- ECG
- TART measured by ultrasound in male participants (results read by central laboratory)
- Sperm count measured at home using a testing kit supplied to the male participants (only in participants who have consented to this assessment)
- Urinalysis
- Sample taken for PRA or PRC, preferably after the participant has been supine for 30 minutes
- Blood sample for HbA1c, FSH, osteocalcin, LH, 11-ketotestosterone, total testosterone, DHEA, and routine biochemistry and hematology
- Pregnancy test in WOCBP (either urine or blood as per the site's usual practice)
- Review of emergency treatment pack for compliance
- Blood sampling for measurement of androgen levels (17-OHP and A4) at 08.00 (pre-dose) and 13.00 hours
- Saliva samples collected for exploratory analysis at 08.00 (pre-dose) and 13.00 hours (optional).

The androgen blood samples are to be taken within ± 30 minutes of the stated timepoints, with the exact sampling times recorded in the eCRF. All samples taken at the EOS visit will be shipped to the central laboratory in the same shipment. Half of the samples will be analyzed and half will be sent on to the biobank for long-term storage and possible future research. Once the last blood sample has been taken at 13:00 hours and all other assessments have been completed, the participant will be discharged from the clinic. At this point the participants can either return to the CAH medication they were taking prior to the study or if they have completed the study with up to 28 weeks of randomized treatment, they can enter an open-label extension study and receive Chronocort (to be conducted under a separate protocol

DIUR-015) or they will be offered commercial supplies of Chronocort. The options will be dependent on territory.

8.1.11. Telephone Call T6.1 (Visit 6 + 30 Days ± 1 Week)

Participants who do not enter the open-label extension study will be contacted by telephone by the local site staff approximately 30 days after Visit 6 to ask about any AEs that were ongoing at Visit 6 and any new SAEs that could be related to the study medication. Any AEs or SAEs reported will be recorded in the eCRF and any SAEs will be reported to the pharmacovigilance group using the paper SAE form.

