The EOS visit will be conducted 28 weeks after randomization or at early withdrawal from the study. The total study duration is up to 40 weeks (screening period up to 4 weeks prior to the screening visit, 4 weeks run-in period on IRHC up to the baseline visit, 16 weeks dose titration on randomized treatment, 12 weeks fixed dose period on randomized treatment, and follow-up phone call 4 weeks/30 days after the EOS visit). In some cases (e.g., if the participant lives a long way from the study site, or if pandemic guidelines dictate) Visits 3 and 4 may be performed as domiciliary visits and IMP shipments can be made directly to the participant's home. However, the following visits must be performed at the study site: Screening (Visit 1), Baseline (Visit 2), Week 16 (Visit 5), and end of treatment/early withdrawal visit (Visit 6). If necessary in some cases, IMP at Visit 5 can also be delivered to the participant's home. If a domiciliary visit is conducted the safety and endocrine blood samples must be sent to the central laboratory for analysis and the Investigator must complete the adrenal insufficiency checklist. The assessment of hirsutism and acne can be conducted via a video call (within ± 2 days of the domiciliary visit). If androgen samples are analyzed locally for safety reasons the participant must be withdrawn from treatment.

At the end of the study, participants who have completed the study will be offered the option of continuing in a long-term safety study (DIUR-015) where all participants will receive open-label Chronocort treatment or they will be offered commercial supplies of Chronocort (the options will be dependent on territory), or the participant can return to the standard treatment they were receiving before entry into this study. For participants who agree to enter the long-term safety study DIUR-015, the EOS visit (Visit 6) will be their last assessment in this study. Participants who decide not to enter the long-term safety study or who withdrew from the study early will receive a telephone call 30 days after the last study visit to ask about any AEs that were ongoing and any new serious adverse events (SAEs) that could be related to the study medication. This telephone call will be considered the last assessment for these participants, although ongoing SAEs will be followed until resolution or stabilization, the event is otherwise explained, or the participant is lost to follow-up.

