8.4.1. Time Period and Frequency for Collecting AE and SAE Information

All AEs and SAEs will be collected for all participants from the time of signing the ICF up to the EOS visit (Visit 6) in participants who are entering the open-label extension study or early withdrawal visit (if applicable), or to the final telephone call T6.1 (approximately 30 days following the last visit) in participants who are not entering the open-label extension study. AEs must be reported equally for both study treatments, regardless of whether the Investigator thinks the AEs are related to the study treatment. Any AEs or SAEs still ongoing at the final visit will be followed until resolution or stabilization if resolution is not expected.

Medical occurrences that begin before the start of study treatment but after the ICF is signed will be recorded on the Medical History/Current Medical Conditions section of the eCRF, not the AE section.

All SAEs will be recorded and reported to the Sponsor or designee within 24 hours, as indicated in Appendix 3. The Investigator will submit any updated SAE data to the Sponsor within 24 hours of it being available.

After the final visit or telephone call, Investigators are not obligated to actively seek AEs or SAEs in former study participants. However, if the Investigator learns of any SAE, including a death, at any time after a participant has been discharged from the study, and he/she

considers the event to be reasonably related to the study treatment or study participation, the Investigator must promptly notify the Sponsor.

The method of recording, evaluating, and assessing causality of AEs and SAEs and the procedures for completing and transmitting SAE reports are provided in Appendix 3.

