#### 5.12.2 Adverse Events

A treatment emergent adverse event (TEAE) is defined as:

- Any AE that has an onset on or after the first dose of study drug and before last dose of study drug + 30 days.
- Any pre-existing AE that has worsened in severity on or after the first dose of study drug and before the last dose of study drug + 30 days.

A TEAE which starts or worsens on or after the first dose of IRHC in the run-in period but before the first dose of randomized study treatment is allocated to the run-in period. A TEAE which starts or worsens after the first dose of randomized study treatment is allocated to the treatment actually received during the randomized treatment period. A TEAE which starts or worsens in the run-in period and worsens in the randomized treatment period is allocated to both periods.

A treatment-related AE is defined as an AE that is recorded by the Investigator as definitely, probably, possibly or likely to be related to the study drug. If an AE has missing relationship it is assumed to be related to the study drug for analysis purposes. Maximum severity will be assumed for an AE with missing severity.

TEAEs will be summarized separately for the run-in period and after randomization. In the list of AE tables below, only the first 2 will be done for both the run-in period and after randomization. All the others will just be done after randomization.

The following tables will be presented for AEs by treatment group:

- Overall incidence and the number of AEs, Serious Adverse Events (SAEs), Treatment related TEAEs, TEAEs leading to withdrawal of study drug, TEAEs leading to early withdrawal from study, TEAEs leading to study drug dose increase or decrease, TEAEs leading to study drug dose interruption, TEAEs leading to use of rescue medication, Treatment Emergent AEs of Special Interest (TEAESIs), non-treatment emergent AEs occurring > 30 days after last dose of study drug, and AEs leading to death run-in period and after randomization
- TEAEs by system organ class (SOC) and preferred term (PT), incidence and number of events run-in period and after randomization
- Treatment related TEAEs by SOC and PT, incidence and number of events after randomization only
- Serious TEAEs by SOC and PT, incidence and number of events after randomization only
- TEAEs by SOC, PT and maximum severity, incidence after randomization only

- Treatment related TEAEs by SOC, PT and maximum severity, incidence after randomization only

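### The 30-day call T6.1 is worded more narrowly than the AE collection rules, and the TEAE definition counts a 30-day tail that is not collected in the same way for all participants

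*Protocol*

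**What the plan says.** Two sets of protocol text describe the last safety contact.

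- **Narrow wording.** Section 8.1.11 has sites telephone participants who do not enter the extension "to ask about any AEs that were ongoing at Visit 6 and any new SAEs that could be related to the study medication". The Synopsis has the call made "to ask about any AEs that were ongoing and any new serious adverse events (SAEs) that could be related to the study medication", and Sections 4.1 and 4.6 say the same.
- **Wide wording.** Section 8.4 has participants asked about any AE at every visit and on every call. Section 8.4.1 collects all AEs and SAEs "up to the EOS visit (Visit 6) in participants who are entering the open-label extension study", "or to the final telephone call T6.1 (approximately 30 days following the last visit) in participants who are not entering the open-label extension study". It adds that "AEs must be reported equally for both study treatments, regardless of whether the Investigator thinks the AEs are related to the study treatment". The AE row of the Schedule of Activities (1.3) is marked at T6.1.

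The analysis rule is separate. SAP 5.12.2 defines a treatment-emergent AE (TEAE) as "Any AE that has an onset on or after the first dose of study drug and before last dose of study drug + 30 days", and also counts pre-existing events that worsen in that period. SAP 5.12.1 and Protocol 9.4.2.6 agree. None of them makes an exception for extension entrants, although Protocol 4.6 ends data collection in this study when a participant moves to the extension. SAP Section 8, which lists changes from the protocol analysis, does not mention the point.

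**The concern.** A site working from its visit section would have no instruction at T6.1 to ask about a new non-serious AE, or about an SAE that it does not think related. A site working from 8.4 and 8.4.1 would ask about both. The other scheduled calls (8.1.4, 8.1.6, 8.1.8, 8.1.9) ask about any AEs; only T6.1 is narrowed.

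The TEAE tables then treat the 30 days after last dose as if they were observed alike in everyone. How much of that tail is observed depends on a choice made after randomization (entering the extension or not) and on which section the site follows. Two features of the plan make this matter for the between-arm tables:

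- SAP 5.12.2 assigns each post-randomization TEAE to the treatment received in the randomized period. After Visit 6, completers may take Chronocort in the extension or as commercial supply, or return to their previous medication (8.1.10). A tail event may therefore be counted against one product while the participant takes another.
- Events of special interest include anything that triggers stress dosing (8.4.8), and these have their own TEAE table. A new non-serious event of that kind after Visit 6 falls outside the narrow T6.1 questions.

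**Working it through.** The plan states no figure to reproduce. The check sets the collection rules against the analysis window and counts days.

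**Inputs**
- Last dose for completers: the morning of Visit 6 (8.1.10). The TEAE tail is therefore the 30 days from Visit 6.
- Timing of T6.1: Visit 6 + 30 days ± 7 days, which gives 30 − 7 = day 23 to 30 + 7 = day 37.
- Extension entrants: collection ends at Visit 6 (4.6, 8.4.1).

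**Coverage of the 30-day tail for completers**

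| Group | Text followed | New AEs solicited |
|---|---|---|
| Not entering the extension | 8.1.11 | Only SAEs that could be related; other new events, 0 of 30 days |
| Not entering the extension | 8.4 and 8.4.1 | All AEs to the call: 23 to 30 of 30 days, so up to 30 − 23 = 7 days missed |
| Entering the extension | 4.6 and 8.4.1 | None in this study: 0 of 30 days |

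**Participants who stop treatment early.** Under 7.1 they are kept in the study, if they consent, with safety assessments on schedule. A participant who stops at Week 16 has 28 − 16 = 12 weeks, or 84 days, of scheduled follow-up left, so the tail can be covered.

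**Participants who withdraw from the study.** The text conflicts here too. Section 8.4.1 names the early withdrawal visit as an end of collection, while the Synopsis and 4.1 give these participants the 30-day call.

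**Can the call still be changed?** Randomization was to stop by 30 April 2023 (9.2). Adding 28 + 1 weeks (203 days) gives 19 November 2023 for the last Visit 6, and adding 37 days gives 26 December 2023 for the last T6.1. If the cut-off was applied at the start of the 4-week run-in instead, adding 28 days gives 23 January 2024. Both dates precede SAP version 4.0 (22 February 2024), apart from any visits postponed for stress dosing.

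**The case against.** The strongest reply is that the wider text governs. Section 8.4 covers every call, 8.4.1 sets the collection period, the Schedule marks AEs at T6.1, and 8.4.2 prefers open-ended questioning. Section 8.1.11 itself goes on to say that AEs or SAEs reported on the call are recorded, with no limit to related or ongoing events. This stands in part: loss of events is not certain and depends on which text sites follow. But recording what a participant volunteers is not the same as asking, and four places in the protocol give the narrow instruction.

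Stopping at Visit 6 for extension entrants is also a stated and defensible choice, since they move to open-label treatment under another protocol. That stands as well. What is missing is a matching end to the TEAE window.

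Three stronger readings are tempting and are not supported:

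- A reader might infer that the TEAE window is complete for nobody and empty for extension entrants. The window opens at first dose and is collected throughout treatment in everyone; only the 30-day tail is in doubt. Early stoppers who stay in the study can be covered.
- A reader might compute 30/(196 + 30) = 13.3%, with 28 × 7 = 196, and take it as the share of TEAEs lost. It is a share of calendar time for a completer, not of events, and it merges groups with different coverage.
- A reader might infer biased safety comparisons because extension entry could follow response. The documents give no extension uptake and no AE rate, and the post-study options depend on territory.

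**Conclusion.** The contradiction about T6.1 is in the current protocol text and is not resolved elsewhere. Separately, the TEAE definition reaches 30 days past last dose for everyone, while collection does not: 0 of 30 days for completers entering the extension, and between 0 and 30 days for new non-serious or unrelated events in other completers, depending on the text followed and the call date. This assumes that completers take their last dose on the day of Visit 6, as 8.1.10 states.

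The number of events affected cannot be computed from the documents. A difference between arms would need uneven extension entry or uneven site practice; that is possible but not shown. The primary and key secondary efficacy inference is unaffected. This is a minor point about safety reporting, worth correcting because the correction is cheap.

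**What to change.** **Protocol.** Reword the Synopsis, 4.1, 4.6 and 8.1.11 so that T6.1 asks about all new AEs and SAEs regardless of relatedness, as 8.4 and 8.4.1 already require. In 8.4.1, reconcile the early withdrawal visit as an end of collection with the 30-day call that the Synopsis and 4.1 give to early withdrawals.

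**SAP.** In 5.12.2, end the main between-arm TEAE tables at Visit 6 for completers. Present later events, up to last dose plus 30 days, separately for the participants who were followed, and state that this period was not collected in all participants. Record the change in Section 8 as a departure from the TEAE definition in Protocol 9.4.2.6.

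**Cost.** A few more minor AEs to record on a call that is already made, and one extra table or listing. Events after Visit 6 in completers leave the main tables, which is why they need their own display. If the calls are already finished, as the dates suggest, only the SAP part can be acted on, and it needs no new data.
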